**Table 3: ISway: data in non-fallers (n=5) and falling PD (n=6). Means + SD.**

	Non-Faller	Faller	t-test (p-value)
Jerk	0.082 ± 0.080	0.213 ± 0.125	t = -2.0 (0.072)
RMS	0.058 ± 0.021	0.109 ± 0.045	t = -2.3 (0.045)
Velocity	0.114 ± 0.050	0.200 ± 0.067	t = -2.3 (0.049)
Centroid Freq (AP)	0.734 ± 0.160	0.617 ± 0.140	t=2.7, (0.026)

ABT-089 on levodopa induced dyskinesias close to 2 weeks after dose cessation, well beyond the  $t_{1/2}$  of this agent. This wash-out interval was used also in the recent VCN AD trial (89). The randomization schedule and process will be prepared by the **Biostatistics and Data Management Core**. Blinded, encapsulated study drug (VCN and placebo) will be supplied by the U-M Research Pharmacy to the study coordinator. The latter will dispense the study medication. Subjects will be evaluated in the University of Michigan Functional Neuroimaging, Cognitive and Mobility Laboratory (see **Facilities and Resources**). Subjects will be directly observed for 3 hours after initial VCN dose and with phone follow-up calls 1-2 business days after starting the medication treatment period, and weekly thereafter. Follow-up phone calls will be completed within a two business day window before or after the target date. VCN plasma levels will be evaluated at end of both treatment periods on days 22 and 64 through a blood draw to monitor compliance. Blood samples will be stored at the University of Michigan Functional Neuroimaging, Cognitive & Mobility Laboratory until the study is finished. Data will be recorded on standard eCRFs and entered into the database for management and analysis by the **Biostatistics and Data Management Core**. Adverse events will be classified by organ system and assessed for causality. All potential possible adverse events will be discussed by the Executive Committee, and reported promptly to the IRB and NINDS.

Gait speed and postural control will be assessed at baseline, at the end of the first VCN/placebo administration period, at the end of the washout period, and at the end of the second VCN/placebo administration period. Gait and postural control will be assessed by the **Clinical Resource Core (Core B)** using the Mobility Lab system that is already established (see Table 3; methodology for Mobility Lab will be as described in detail in Project II). MDS-UPDRS, Geriatric Depression Scale, Montreal Cognitive Assessment, WAIS Digit Span and Digit Symbol coding tests, and D-KEFS executive function/working memory tests will be administered as part of the evaluations. Subjects will be screened for suicidality with the C-SSRS before VCN treatment, weekly during phone follow-up, and at the end of treatment-washout periods.

**Figure 5: Schematic Timeline for Experiment 3**

**Sample Size:** The main basis for the sample size for this 2-sequence, 2-period, 2-treatment crossover study is based on gait speed and the postural control parameter, ACC JERK. Both endpoints are considered primary and so a Bonferroni adjustment will be made to control the Type I error for the study at the one-sided 1.5% level (i.e., each endpoint will be tested at the 0.025 level). Published (56) and preliminary data in PD subjects (**Table 2**) provide estimates of effect and variability for these parameters in the placebo group. We powered our study based on conservative estimates derived from these data (i.e., using the 95% upper confidence bound of the SD as the estimate of variability in the sample size calculations) and the desire to detect at least a 10% relative treatment effect in gait speed and 60% relative treatment effect in ACC JERK. With a total of 33 subjects, we have at least 80% power to detect a treatment difference between VCN and placebo of 0.112 m/s and -0.131 m^2/s with a Bonferroni-adjusted two-sided Type I error of 2.5%, assuming within-subject correlation of at least 0.64 and 0.72, respectively (a conservative estimate given that test-retest correlation of ACC JERK in PD subjects was 0.86[97]). We will enroll 42 subjects to allow for a 10% attrition rate. We will examine some pre-defined secondary endpoints; RMS (root mean square of center of pressure variability), gait speed variability, and anterior-posterior sway velocity. These secondary endpoints are chosen on the basis of published data with ISway (97), and preliminary data (**Table 2**), and additional preliminary data suggesting association of gait speed variability and anterior-posterior sway velocity with deficits of specific cholinergic pathways (**Project II** preliminary data). We will use a gatekeeper testing strategy to control the familywise error for the secondary endpoints that play a supportive role in interpreting the effects of VCN (105,106). If at least one of the primary endpoints is significant (at least one of the hypotheses is rejected), hypotheses for the secondary endpoints will be tested using Hochberg's step-up method (107). This approach ensures the overall Type I error rate is no greater than 0.05.

**Analysis Method.** For all aims, we will conduct exploratory analyses to examine the distributions of outcomes under each treatment, as well as individual and mean profiles over time. Graphical approaches such as boxplots and scatterplots with linear or non-linear (e.g., loess) methods will be used, allowing identification of outliers, linearity, and correlation of measurements within person and across time. If outcome data do not appear normally distributed, transformations will be employed. Because participants' outcomes will be measured at more than one time point per

person, our analyses will be based on linear mixed effects models (108-110). We expect no carryover since treatments will be spaced three weeks apart. Tests to compare treatments will be based on Wald and chi-squared tests based on maximum likelihood or restricted maximum likelihood methods. Alternative covariance structures (other than compound symmetry) will also be explored and model fit examined using the Akaike Information Criteria (AIC).

[figure not shown]
**Potential Problems and Alternatives:** All measures proposed for this experiment are well established in the University of Michigan Functional Neuroimaging, Cognitive and Mobility Laboratory and the **Clinical Resource Core**. The major foreseeable difficulties are subject recruitment and retention. We've had considerable success recruiting and retaining subjects in protocols involving up to 4 PET studies, serial evaluations, long-term follow-up (months to years), and subject clinical-psychometric-gait & balance evaluations as intensive as those proposed. We budget a 10% drop out rate in this study, which is typical of our experience in prior prospective studies and identical to the dropout rate in the recent AD study (89). A related concern would be unexpected difficulty with VCN tolerability, leading to excessive dropouts. The goal of the SA1 experiments is to find the lowest dose providing high  $\alpha 4\beta 2^*$  nAChR occupancy, which provides protection against this possibility. In the recent AD study, VCN was tolerated well at higher doses than we expect to employ. If tolerability is a problem, we would use a slower dose escalation regimen.

It is possible that there will be differential effects of VCN on gait speed and postural control. We will be drawing these subjects from **Project II**, where all participants will receive anatomically resolute  $[^{18}\text{F}]$ FEBOV imaging. As discussed in **Project II**, there may be correlates between specific pathway deficits, such as BF projection versus PPN projection degeneration, or even more specific pathway changes such as PPN to cerebellar vermis projection deficits, and specific gait or postural control measures (see **Project II** Preliminary Data). We will have a rich dataset to examine these possibilities, including not only imaging data but also the considerable gait and balance data generated by the Mobility Laboratory system for exploratory analyses. It is possible that VCN will have no effect on gait, balance, or cognition in these subjects. This would be disappointing but important as it would steer the field towards other types of cholinergic receptors as therapeutic targets. Comparison of these results with parallel **Project I** experiments will also be important for evaluating the novel model developed in that Project.

**Specific Aim 3:** To assess the effects of pharmacologic  $\alpha 4\beta 2^*$  nAChR activation on a measure of attentional function (SAT; sustained attention test) in PD subjects with cholinergic deficits.

**Rationale and Predictions:** Our preclinical work with a novel rodent model of cholinergic-dopaminergic gait deficits indicates that diminished attentional function following loss of corticopetal BF afferents is a key mediator of the effects of cholinergic system degeneration on gait and balance (**Overview; Project 1**). A large body of prior research indicates attentional function impairments contribute significantly to impaired gait and postural control, including falls, in normal elderly and PD patients (33-39). In a recent large prospective study, for example, attentional function deficits predicted falls in older adults (39). [name] extensive prior work indicates that  $\alpha 4\beta 2^*$  nAChRs are crucial actors in cholinergic modulation of attention (**Project 1**) (42-46). Consistent with this work, our preliminary preclinical data suggests that stimulation of  $\alpha 4\beta 2^*$  nAChRs improves gait and balance in the novel dual lesion model (**Project 1**). These combined results lead to an important prediction: subacute  $\alpha 4\beta 2^*$  nAChR administration to hypocholinergic PD subjects will improve attentional performance and improved attentional performance will correlate with improved gait and postural control induced by  $\alpha 4\beta 2^*$  nAChR stimulation. Evaluating this prediction is important for assessing the mechanisms by which cholinergic projection system degeneration impairs gait and balance and is important also for assessing the validity of the novel rodent model presented in **Project 1**.

**Preliminary Data:** [name] group developed a robust test of attentional function, the Sustained Attention Test (SAT), for use in rodent experiments, and subsequently adapted and validated the SAT for use in humans (**Project 1**) (111-113). Briefly the SAT consists of a randomized sequence of cued and non-cued (or signal and nonsignal) trials. Responses are hits and misses, and correct rejections and false alarms, respectively. Hits and correct rejections are rewarded. SAT performance reflects frontal cortical cholinergic signaling through  $\alpha 4\beta 2^*$  nAChRs. We evaluated a particularly relevant version of the SAT including a distractor component (dSAT), in PD subjects who had previously undergone  $[^{11}\text{C}]$ PMP imaging to assess cholinergic projection systems integrity. There was considerable variation in dSAT performance, which was a linear function of cortical cholinergic terminal integrity (**Figure 6**). These results indicate that dSAT performance in PD directly reflects cortical cholinergic signaling, likely mediated by  $\alpha 4\beta 2^*$  nAChRs.

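### When one primary and all three secondaries are won, half of the stated 0.05 goes unused; a final retest of the other primary would use it at no cost, once the Hochberg level is stated

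*Protocol*

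**What the plan says.** The rules are in the Sample Size paragraph of the protocol's Specific Aim 2, below the caption of Figure 5.

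- **Primaries.** Gait speed and ACC JERK: "Both endpoints are considered primary and so a Bonferroni adjustment will be made". The level is given as "each endpoint will be tested at the 0.025 level", and power is computed "with a Bonferroni-adjusted two-sided Type I error of 2.5" per cent.
- **Secondaries.** They open on this condition: "If at least one of the primary endpoints is significant (at least one of the hypotheses is rejected"). Then "hypotheses for the secondary endpoints will be tested using Hochberg's step-up method". There are three: "RMS (root mean square of center of pressure variability), gait speed variability, and anterior-posterior sway velocity". No alpha level is given for the Hochberg step.
- **Overall claim.** "This approach ensures the overall Type I error rate is no greater than 0.05". The same paragraph also says it will "control the Type I error for the study at the one-sided 1.5% level", which agrees neither with 0.025 per endpoint nor with 0.05 overall.

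Nothing returns alpha to the primary that was not won. The SAP covers only the two occupancy experiments. Its section 4.1 treats the crossover as a future study, and it has no multiplicity rule for it.

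**The concern.** Hypothesis 2 predicts improvement in both gait function and postural control. Under a fixed split, the second primary faces 0.025 even after every other hypothesis in the family has been rejected. At that point it is the only hypothesis left, and 0.05 could be spent on it. If its p-value lies between 0.025 and 0.05, a true effect on both outcomes is reported as an effect on one. The protocol's Specific Aim 2, Potential Problems and Alternatives, treats differential effects on gait and postural control as informative, so such a miss could be read as a real dissociation.

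**Working it through.** **1. The plan's own figure.** JERK SD in fallers is 0.125, n = 6 (Table 3). The upper limit of the two-sided 95% interval is 0.125 × √(5/0.831) = 0.307. With within-subject correlation 0.72, the SD of the difference is 0.307 × √(2 × 0.28) = 0.230. For an effect of 0.131 at two-sided 0.025, noncentral t gives N = 32, and 81.7% power at N = 33. The stated 33 subjects and at least 80% power are reproduced. No gait speed SD is given, so that endpoint cannot be checked. The split 0.025 + 0.025 = 0.05 matches the overall claim.

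**2. Unused alpha.** If the remaining primary is the only true null and all else is won, familywise error is P(p ≤ 0.025) = 0.025, half of 0.05.

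**3. Is a final retest at 0.05 safe?** Three cases cover every configuration with a true null primary or secondary:
- *Some secondary is a true null.* The retest happens only after that secondary has been rejected, so an error has already been counted.
- *Both primaries are true nulls.* The retest happens only after one has been rejected, so again an error has already been counted.
- *One primary is the only true null.* Error is at most P(p ≤ 0.05) = 0.05.

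The step comes last, so it cannot undo a rejection. Simulation (one million replicates per scenario, correlation 0 and 0.5) agrees: error goes from 0.025 to 0.050 in the third case and is unchanged elsewhere.

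**4. The Hochberg level matters first.** Suppose one primary is certain to be won, and the other primary and one secondary are true nulls and independent.
- Hochberg at the 0.025 passed on: 1 − 0.975 × 0.975 = 0.049.
- Hochberg at full 0.05 after one win: 1 − 0.975 × 0.95 = 0.074. Simulation gives about 0.073 with all three secondaries null, with or without the retest.

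**5. Size of the gain.** Power of 80% at two-sided 0.025 means noncentrality 2.241 + 0.842 = 3.083. At 0.05 that gives Φ(3.083 − 1.960) = 86.9%, so 6.9% of the distribution lies between the two thresholds. Hochberg at 0.025 rejects all three secondaries only if all three p-values are ≤ 0.025. With independence and equally strong secondaries:
- Both primaries, plan: 0.8² = 64.0%.
- Added by the retest: 2 × 0.8 × 0.0693 × 0.8³ = 5.7 points, giving 69.7%.
- Each primary: half of that, 2.8 points, giving 82.8%.

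With secondaries at noncentrality 2.0, the power of each at 0.025 is Φ(2.0 − 2.241) = 40.5%. The gain in both is 2 × 0.8 × 0.0693 × 0.405³ = 0.7 points.

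Simulation with equal correlations:

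| Correlation | Both, plan | Both, retest, equal secondaries | Each primary, retest, equal secondaries | Gain in both, secondaries at 2.0 |
|---|---|---|---|---|
| 0 | 64.1% | 69.8% | 82.9% | 0.7 points |
| 0.3 | 66.6% | 71.3% | 82.4% | 0.6 points |
| 0.5 | 68.7% | 72.9% | 82.0% | 0.4 points |

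Between the two extremes, secondaries with 80% power at 0.05 give a gain in both of 4.0, 3.3 and 2.7 points.

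**6. If primary power exceeds 80%.** At 87% per primary, 5.0% lies between the thresholds. With each secondary still at 80% power, the gain in both falls to 2 × 0.87 × 0.0504 × 0.8³ = 4.5 points. If the secondaries strengthen equally, it is 2 × 0.87 × 0.0504 × 0.87³ = 5.8 points. By 93% power throughout it is down to 2 × 0.93 × 0.0306 × 0.93³ = 4.6 points.

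**The case against.** The case for leaving the plan alone has four parts.

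- **Nothing is broken.** Bonferroni controls error across the two primaries, and 33 subjects were sized at 0.025. This stands: the point concerns efficiency only.
- **Winning both is not the success rule.** One primary win suffices, and this is a pilot target-engagement study. At 80% each and independence, the chance of at least one win is 1 − 0.2² = 96%. This stands. A reader might take 64–69% for both as a sign of underpowering, but the documents never set that target.
- **The gain depends on the secondaries.** The documents give no treatment effects for them and no correlations between endpoints, so the 4–6 point figure assumes strong secondaries. This stands. Power is also a floor: it uses an upper bound for the SD, and 42 enrolled less 10% is about 38 evaluable, not 33. With secondary power held fixed, that shrinks the gain (step 6).
- **The won primary's alpha is not idle.** It pays for the secondary tests. This stands against returning alpha straight away, but not against a retest that waits until all three secondaries have been rejected.

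The immediate-return version, Holm on the primaries with secondaries opened only after both, may look like the better remedy. It lifts both primaries to 75.2% at zero correlation, but each secondary drops from 79.1% to 64.0% (at correlation 0.6, from 76.9% to 72.4%). That is a trade-off and is not recommended here.

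**Conclusion.** The point holds as a minor, optional improvement. The protocol returns no alpha to the other primary, and a retest after one primary and all three secondaries are won costs no rejection and keeps familywise error at or below 0.05, provided the Hochberg level is settled first.

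The gain in winning both primaries is about 4–6 points if the secondaries are as strong as the primaries, and under 1 point at noncentrality 2.0. Each primary gains about 0–3 points. This assumes 80% power per primary at 0.025, equal correlations of 0 to 0.5, and 0.05 as the overall level.

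Two stronger readings are not supported. One might infer that the second primary would have 87% power, but that applies only once everything else has been won. One might also infer that the plan exceeds 0.05. That follows only if Hochberg runs at full 0.05 after a single win, and the text neither says so nor rules it out. Equally, the rule of passing on 0.025 per primary won is not in the text and has to be added. The crossover's detailed analysis plan is not among the documents, so the finding concerns the protocol text alone.

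**What to change.** Before unblinding, in the crossover's analysis plan and the Sample Size paragraph:

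1. State that Hochberg on the three secondaries runs at the alpha passed on from the primaries won: 0.025 after one, 0.05 after both.
2. Add: if one primary and all three secondaries are rejected, the remaining primary is retested at two-sided 0.05.
3. In the same edit, reconcile the one-sided 1.5% statement with 0.025 per endpoint and 0.05 overall.

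The cost is a few sentences. Sample size, visits and data collection do not change. If item 1 is not adopted, item 2 does not make error worse in the cases where it already exceeds 0.05, but it does not repair them either.

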**Figure 6: Correlation of cortical cholinesterase with dSAT**

**Procedures:** This experiment will be conducted in parallel with those for SA2. Attention will be evaluated with the dSAT at all evaluation points in the double-blind crossover design VCN intervention study described above. We will correlate dSAT changes in response to VCN with gait speed and postural control changes in response to VCN. The sample size is determined from the goals of **SA2**. With this sample size, an effect size of 0.4 can be detected with at least 80% power and a two-sided Type I error of 0.05 assuming a within-subject correlation of 0.69. Similar statistical methods as those used for SA2 will be employed to test the impact of VCN on dSAT. An exploratory analysis will be conducted to examine medication of treatment effects on gait and other postural outcomes by dSAT. In the presence of a treatment effect, a variable is declared a mediator if it complies with three things: it is affected by the treatment, it predicts the endpoint of interest, and the treatment effect is attenuated when the potential mediating factor is adjusted for. Mediation analysis will be conducted by including mediating factors in the mixed model regression analysis outlined above. Structural equation models will be used to estimate the direct effect of VCN and the indirect effects of the VCN due to mediators, as has been recommended for intervention studies of disease prevention (114,115).

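### The primary crossover tests are planned as Wald and chi-squared tests with no small-sample reference, so as written they run modestly above the promised 0.025 per endpoint

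*Protocol*

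**What the plan says.** The protocol sets the test in the Analysis Method paragraph of Specific Aim 2: "Tests to compare treatments will be based on Wald and chi-squared tests based on maximum likelihood or restricted maximum likelihood methods". The model is a linear mixed-effects model. Compound symmetry is the implied default, and other covariance structures are to be explored by AIC. The paragraph does not say that the structure with the best AIC becomes the basis for inference.

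The Sample Size paragraph of the same aim sets the standard the test has to meet. The power claim reads "With a total of 33 subjects, we have at least 80% power" and is made "with a Bonferroni-adjusted two-sided Type I error of 2.5%, assuming within-subject correlation of at least 0.64 and 0.72". After describing the gatekeeping scheme for secondary endpoints it concludes: "This approach ensures the overall Type I error rate is no greater than 0.05". On numbers it adds: "We will enroll 42 subjects to allow for a 10% attrition rate".

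The Procedures paragraph of Specific Aim 2 lists four assessments: baseline, end of period 1, end of washout and end of period 2. The Analysis Method does not say whether all four or only the two end-of-period values enter the model. For the attention test, Specific Aim 3 says: "Similar statistical methods as those used for SA2 will be employed to test the impact of VCN on dSAT".

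The SAP does not settle the matter. It covers the PET occupancy experiments, plans descriptive statistics for them (section 8), and treats the crossover as a later study (section 4.1).

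**The concern.** A Wald statistic divides the estimated treatment effect by an estimated standard error. Referring it to the normal or chi-squared distribution treats that standard error as known. With 33 to 38 subjects it is not known well enough for that, and the test rejects too often. ML makes this worse, because it divides the residual sum of squares by the number of observations without deducting the fixed effects.

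A chi-squared test with no degrees-of-freedom method supplies no correction. At stake is the explicit promise of 0.025 per endpoint, and through the Bonferroni split the promise of 0.05 overall. Two further open choices, ML or REML and two visits or four, also move the error rate and could be settled after the data are seen.

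**Working it through.** **Inputs.** Two-sided alpha is 0.025 per endpoint, so z = 2.2414. N = 33 is the power calculation's figure. Completers: 42 × 0.9 = 37.8, about 38. All of these come from Specific Aim 2, Sample Size. For Specific Aim 3, alpha is 0.05 and z = 1.960.

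**The plan's own power first.** I used SE = SD·√(2(1−ρ)/n) and a noncentral t with n−2 df.

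- JERK: the planned difference of 0.131 equals 0.213 − 0.082 in Table 3. I assume the SD comes from the fallers (0.125, n = 6). The upper limit of a two-sided 95% interval is 0.125·√(5/0.831) = 0.307. With ρ = 0.72 and n = 33, SE = 0.0399, noncentrality = 3.28 and power = 81.7%.
- JERK with a one-sided 95% bound: SD = 0.125·√(5/1.145) = 0.261 and power = 92.7%.
- Specific Aim 3: effect 0.4, ρ = 0.69, power = 80.7%.

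These agree with the claim of at least 80%. Gait speed cannot be checked because its SD is not in the documents.

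**Actual error on a normal or chi-squared reference.** With complete end-of-period data, the treatment estimate has an exact t distribution with n−2 df. With four visits, compound symmetry, and baseline and washout counted as untreated, the df are 3n−4. Write f for the df and m for n (two values) or 3n (four visits):

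- REML Wald: P(|t_f| > z)
- ML Wald: P(|t_f| > z·√(f/m))
- ML likelihood ratio: P(|t_f| > √(f·(exp(z²/m) − 1)))

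Example, n = 33 and two values: f = 31. The effective cut-offs are 2.241, 2.241 × √(31/33) = 2.172, and 2.258. The correct t cut-off is 2.356.

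| Data used | n | df | REML Wald | ML Wald | ML LR | t cut-off |
|---|---|---|---|---|---|---|
| End of period | 33 | 31 | 0.0323 | 0.0376 | 0.0311 | 2.36 |
| End of period | 38 | 36 | 0.0313 | 0.0357 | 0.0303 | 2.34 |
| Four visits | 33 | 95 | 0.0273 | 0.0306 | 0.0285 | 2.28 |
| Four visits | 38 | 110 | 0.0270 | 0.0298 | 0.0280 | 2.27 |

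Simulation agrees. For two values (400,000 null trials per n), REML and ML Wald give 0.0321 and 0.0373 at n = 33, and 0.0312 and 0.0357 at n = 38. A t reference gives 0.0246 and 0.0249. For four visits (40,000 null trials), n = 33 gives 0.0274 and 0.0305, with 0.0251 on a t reference.

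**Both endpoints together.** Twice the per-endpoint error is an upper bound: 0.055 to 0.075 at n = 33 and 0.054 to 0.071 at n = 38. The actual familywise error falls as the endpoint estimates become more correlated. By simulation it exceeds 0.05 only if the absolute correlation is below about:

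| Data used | n | REML | ML |
|---|---|---|---|
| End of period | 33 | 0.84 | 0.95 |
| End of period | 38 | 0.81 | 0.92 |
| Four visits | 33 | 0.55 | 0.77 |
| Four visits | 38 | 0.52 | 0.73 |

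**Specific Aim 3.** The same formulas at z = 1.960 give 0.053 to 0.067 at n = 33 and 0.053 to 0.064 at n = 38, against a nominal 0.05.

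**The case against.** The strongest reply is that the plan never says the statistics are referred to a normal distribution. "Wald" names a statistic, and mixed-model software can report it with a t or F reference. The power figures even point that way: for Specific Aim 3, 80% power at n = 33 needs a correlation of 0.684 by t and 0.664 by z, and the stated 0.69 sits closer to the first. The minimum N there is 33 by t and 31 by z. This part stands to the extent that the error rates are conditional on the reference distribution. It does not remove the point: a power calculation does not set the analysis rule, and the rule as written names chi-squared tests and no df method.

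It is also fair that the top figure of 0.038 needs ML, end-of-period values only and 33 completers together; that the REML excess is small; and that a breach of 0.05 overall is not shown, since the endpoint correlation is unknown. All three stand. A separate SAP for the crossover might settle the details, but none is among the documents.

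The Sample Size paragraph also mentions a study-level one-sided 1.5%, which conflicts with 0.025 per endpoint. I used the two-sided 0.025 of the power statement; the conflict is a separate matter.

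In the other direction, the range is not a ceiling. It assumes fixed compound symmetry. An unstructured four-visit covariance with a normal reference simulated at about 0.055 (REML) and 0.059 (ML) at n = 33 (6,000 null trials each, Monte Carlo standard error 0.003). The plan only says it will explore other structures, so I do not charge that figure to it.

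**Conclusion.** The concern holds. Followed as written, the plan exceeds its two-sided 0.025 per endpoint in every compound-symmetry version computed, from 0.027 (REML, four visits) to 0.038 (ML, two values, 33 subjects). The promise of 0.05 overall is no longer guaranteed, although whether it fails cannot be determined from the documents. The result rests on a normal or chi-squared reference, normally distributed data, complete pairs and fixed compound symmetry. The excess is modest, but it can be removed at almost no cost, so the change should be made.

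**What to change.** Pre-specify one primary model for both endpoints: REML; random subject; fixed treatment, period (or visit) and sequence; a stated set of visits; one named covariance structure, for example compound symmetry; and t or F tests with Kenward-Roger or Satterthwaite degrees of freedom at two-sided 0.025. Use the same method for dSAT at 0.05. Report ML fits and AIC-selected structures as sensitivity analyses only.

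The cost is one or two sentences and a software option. The critical value rises from 2.24 to at most 2.36. The t-based power figures above stay at or over 80% with 33 subjects: the minimum N is 32 (SD 0.307) or 24 (SD 0.261) for JERK and 33 for Specific Aim 3, against 30, 22 and 31 by z. No extra subjects are needed on these inputs. Gait-speed power should be confirmed by the sponsor, who holds the SD.
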